STUDY SUMMARY

STUDY OVERVIEW	
Full title	Renal function Assessment with Point of Care creatinine In Diverse populations (RAPID)
Objectives	
Study A
 
 • To compare capillary POC-Cr with venous serum enzymatic creatinine concentrations (serum Cr) in people of different ethnicities performed by health care professionals and patients • To compare estimated glomerular filtration rate (eGFR) using POC-Cr and serum Cr with formal GFR assessment in people of different ethnicities • To define a threshold of POC-Cr concentration in different ethnicities which are confirmatory of eGFR <60mls/min/1.73m² (Kidney Disease Improving Global Outcomes; KDIGO Definition Stage 3) and a range of POC-Cr which may require further confirmation 
Study B
 
 • To conduct an observational cohort study of serial capillary self-testing POC-Cr for at least one week. • To compare single and serial capillary POC-Cr compared with single venous creatinine concentration IDMS traceable enzymatic assay • To assess test success rate, safety, training time, patient experience and acceptability of serial capillary POC-Cr testing
Type of trial	Two centre cross-sectional study and prospective longitudinal cohort study
Trial design and methods	
375 participants (including > 40 of African/African-Caribbean ancestry) having venous serum creatinine and 99mTc-DTPA nuclear medicine or venous GFR filtration panel testing will be recruited to a cross sectional study (Study A)
 
At least 40 patients with CKD will be recruited to a longitudinal study (Study B)
 
Demographics, medical and transportation details will be recorded
 
Finger-prick capillary creatinine will be assessed by POC-Cr device; Venous serum creatinine concentration (Isotope Dilution Mass Spectrometry (IDMS) Traceable Enzymatic assay).
 
Participants will be trained to use POC-Cr device, asked to self-monitor up to four times per day and report details including test failure and adverse events.
 
Patient experience and acceptability will be assessed using Service User Technology Acceptability Questionnaire.

Health condition(s) or problem(s) studied	Chronic Kidney Disease
Target sample size	At least patients 415 (Study A: 375; Study B: At least 40)
Trial duration per participant:	Study A: 1 Day Study B: 1 week


Main inclusion/exclusion criteria:
	
Inclusion criteria:
 
 • Is 18 years of age or older • Is willing to complete all study procedures • Study A: Patients undergoing formal nuclear medicine (99mTc-DTPA) glomerular filtration rate testing or willing to have a venous GFR filtration panel (Study A only) • Study B: Has Chronic Kidney disease (CKD) KDIGO criteria or is at risk of CKD due to heart disease or diabetes as determined by physician 
Exclusion criteria:
 
 • Unable or unwilling to give informed consent • Any condition which would make finger prick contraindicated e.g. severe skin conditions, bleeding disorder • Study A: If formal GFR testing has been requested only because estimated GFR is not considered to reflect true GFR (e.g. liver disease)

Statistical methodology and analysis:
	
 • Accuracy compared to venous serum creatinine and 99mTc-DTPA testing or GFR filtration panel will be calculated for POC-Cr capillary blood testing performed by patients and health care professionals. • Total, between-day, and within-day precision will be evaluated by comparing up to four POC-Cr capillary concentrations for at least seven days and compared to day 1 and 8 venous serum creatinine concentrations.

STUDY TIMELINES
	

Study Duration/length
	
End date 30/06/2025

Expected Start Date
	
1/7/20

End of Study definition and anticipated date
	
Last patient completed final study visit

Key Study milestones
	
 • Month 1-28: Recruitment • Month 29: Data analysis • Month 30 Outcome presentation/publication

STORAGE of SAMPLES (if applicable)
	

Human tissue samples
	
N/A

Data collected / Storage
	
Pseudoanonymised data will be stored for 5 years after study completion in secure filing cabinets in the renal research team locked room.

1 BACKGROUND AND RATIONALE

People of black or Asian and minority ethnicities (BAME) have a 3-5 fold increase in requirement for dialysis to treat kidney failure and present with kidney disease at younger ages. Prevention of progression to kidney failure is often possible at earlier stages of kidney disease¹ but kidney disease is often silent until later stages². Frequently people from BAME have more advanced disease at diagnosis with fewer options for treatment. Early detection is likely to reduce the incidence of kidney failure, which currently costs 3% of the total NHS budget. Screening people of high-risk ethnicities has been reported to be cost effective^{3,4} in other countries but the feasibility of community screening of high-risk groups in the UK has not been explored.

Point of care (POC) testing with finger-prick blood monitoring are now available to assess kidney function (creatinine) with the finger-prick method, giving results in less than a minute without additional cost of venous blood-taking, transportation and processing. An Australian screening program with POC-Cr reported that 99% of participants found it convenient and 96% felt that the immediate results and feedback helped them understand their condition better⁵. Opportunities for POC-Cr screening led by allied health care professionals (AHP) before radiological investigations⁶ are being explored and an NIHR 'Horizon scanning report' assessing the potential role of POC-Cr testing for detection and monitoring of CKD⁷ recommended assessment of clinician and patient clinical need but POC-Cr screening for people at high risk of CKD, including ethnic minority groups has not been investigated.

Our recent engagement event hosted by The Africa Advocacy Foundation (AAF) highlighted lack of trust, anxiety and inconvenience attending current health care appointments. Rapid availability of POC-Cr results could provide instant information about kidney health for high-risk groups in the BAME community (e.g. in faith-based settings). This approach was highly welcomed by engagement event participants if sign posting to relevant services and tailored educational material was available. However, there have been conflicting reports of correlation between venous and capillary (finger-prick blood) creatinine concentrations⁸ and no formal assessment of performance POC-Cr in people of different ethnicities' has been undertaken.

Recently, use of ethnicity in kidney function testing has been recommended to be removed. New biomarker GFR filtration panels which do not require adjustment for ethnicity have been

demonstrated to provide better estimation of measured GFR and can be performed without the need for costly nuclear medicine assays⁹. In addition, assessment of lean body weight may enhance estimation equations¹⁰ but have not been assessed in combination with POC-Cr testing.

In other chronic diseases, self-monitoring is associated with feelings of security, reassurance, control, high motivation and levels of satisfaction¹¹ and has transformed care for millions of individuals (e.g. glucose testing). Self-monitoring with POC-Cr testing could empower kidney patients to participate in their own care, enable timely intervention at times of deterioration, and reduce unnecessary hospital visits and damage to veins. Home POC-Cr testing has been demonstrated in a small paediatric study to be an acceptable alternative to hospital testing¹².

Self-monitoring with POC-Cr was strongly supported by AAF engagement participants if appropriate self-care material and education is provided and proposed benefits included privacy of personal monitoring or in a faith-based community setting at the individual's convenience. This approach was considered ideal for those identified to have early CKD at screening event with minimal health care professional contact. However, in order to harness the benefits of POC-Cr self-monitoring it will be important to understand and interpret intra-patient variability in capillary blood results, potentially without need for complete alignment with laboratory tests. Conversely, self-monitoring may introduce increased anxiety and requirement for additional interaction with health care services and concurrent understanding of feasibility (training required, number of successful tests) and patient experience (including acceptability of monitoring frequency) of self-monitoring POC-Cr is critical.

Our overall aim is to develop and pilot a UK community-based screening and CKD monitoring program to address health inequalities in CKD, focusing on people from ethnic minority groups.

Essential preliminary data using hand-held POC-Cr device is required to secure future funding for this work. Hand held POC-Cr has been reported to perform less well than larger 'table-top' POC-Cr devices when capillary blood testing is compared with venous creatinine sampling¹³ but has been chosen for this study because it requires only a finger-prick sample with a simple cheap hand-held device and therefore can easily be used in community settings¹⁴ and by patients¹⁵.

2 OBJECTIVES

2.1 Primary Objectives

Study A

- To compare estimated glomerular filtration rate (eGFR) using POC-Cr and serum Cr with formal GFR assessment in people of different ethnicities.

Study B

- To conduct an observational cohort study of serial capillary self-testing POC-Cr for at least one week.
- To compare capillary POC-Cr with venous serum enzymatic creatinine concentrations (serum Cr) in people of different ethnicities performed by health care professionals.
- To compare serial capillary POC-Cr compared with single venous creatinine concentration IDMS traceable enzymatic assay.

2.2 Secondary Objectives

Study A

- To define a threshold of POC-Cr concentration in people of different ethnicities which are confirmatory of eGFR $<60\text{mls}/\text{min}/1.73\text{m}^2$ (Kidney Disease Improving Global Outcomes; KDIGO Definition Stage 3) and a range of POC-Cr which may require further confirmation.
- To compare capillary POC-Cr with venous serum enzymatic creatinine concentrations (serum Cr) in people of different ethnicities performed by health care professionals

Study B

- To assess test success rate, safety, training time, patient experience and acceptability of serial capillary POC-Cr testing

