3 STUDY DESIGN

Study A: Cross-sectional cohort study

Study B: Observational longitudinal cohort study

Research Ethics Committee approval and R&I approval will be sought for the study. Participants who meet the entry criteria will be recruited and consented by the investigator, or any GCP qualified member of the local research team who has delegated responsibility for study recruitment. Participants will be recruited from King's College Hospital, Royal London Hospital outpatients and wards and nuclear medicine department. Participants will be offered a minimum of 24 hours to reflect on the patient information sheet (PIS), which will be provided during initial discussion. Participants will be selected purposively to include a range of age, gender, ethnicity (at least 50% African/Afro Caribbean), severity of renal disease and clinical settings. Participants in study A will be able to participate in study B if they wish to do so.

Demographics, Body mass index, waist circumference and lean body mass (Fresenius - Body Composition Monitor and clinician estimated), mobility at home, mode of transportation to come to hospital, length and cost of travel, carer details, drug history, number of hospital visits and GP visits per year and reason for laboratory creatinine testing (e.g. monitoring Ig A nephropathy) will be recorded. Data will be transferred following pseudo-anonymisation into a study specific database by the research team.

POC-Cr testing

Capillary POC-Creatinine concentration will be assessed by NovaMaxCreat (NovaBio) and Epoc (Siemens) POC hand-held devices. A quality control will be performed for each POC-Cr device each day by the study nurse and by participants, ensuring the reagent batch conforms the manufacturers' quality specifications. POC reagents will be stored and used following manufacturers' specifications.

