6.1 Inclusion Criteria

- Is 18 years of age or older
- Is willing to complete all study procedures
- Study A: Patients undergoing formal nuclear medicine (99mTc-DTPA) glomerular filtration rate testing or willing to have a venous GFR filtration panel (Study A only)
- Study B: Has Chronic Kidney disease (CKD) KDIGO criteria or is at risk of CKD due to heart disease or diabetes as determined by physician

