8 STATISTICAL METHODS

Study A: Readings taken with measured with NovamaxCreat and Epoc blood analysis system will be analysed separately. Bland-Altman plots and Passing-Bablok regressions will be generated for POC-Cr concentrations using Stata version 21 or later. The analytical error percentage compared to the reference standards (IDMS enzymatic traceable and 99mTc-DTPA and GFR filtration panel) ($=100 \times ([\text{POC device}] - [\text{reference standard}]) / [\text{reference standard}]$) will be calculated for each POC-Cr recording in each participant. In addition, average analytical error percentage and a 95% confidence interval (95%CI) will be calculated following Clinical Laboratory Standards Institute procedures.¹⁶ Criteria used to check analytical error percentage will be derived from the 'Desirable Specifications for Allowable Total Error (ATE)' database for creatinine (ATE=8,87%)¹⁵ and from the Laboratory Working Group of the National Kidney Disease Education Program (NKDEP) for eGFR (ATE=10%)¹⁷. Although the 10% ATE for eGFR is actually a performance specification for creatinine, it has been used in as an acceptable total error for eGFR.^{18,19,20} Categorical agreement of POC-Cr concentrations with the reference standards will be calculated using the unweighted Kappa statistic. Error analysis using predefined minor and major classification errors will be performed for POC-Cr concentrations. POC-Cr concentrations and reference standards will also be assessed by Deming regression and Pearson's correlation coefficient. Bias offset required will be recorded

Proportion of patients correctly identified to have CKD $eGFR < 60 \text{mls/min/1.73m}^2$ will be reported. Sensitivity and Specificity of different Cr thresholds calculated.

Study B: Number of tests attempted per participant, daily frequency of testing and proportion of successful attempts will be reported. Reasons for unsuccessful attempts and adverse events will be described and quantified if appropriate. Time taken to train per patient will be reported in minutes as median and IQR.

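### The Study A threshold for eGFR below 60 is set on raw POC creatinine with ethnicity the only stratifier named; putting age and sex into the rule is a cheap improvement

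*Protocol*

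**What the plan says.** Protocol section 2.2 (Study A), repeated in the Study Summary, sets the objective: "To define a threshold of POC-Cr concentration in people of different ethnicities which are confirmatory of eGFR" below 60 mL/min/1.73 m², "and a range of POC-Cr which may require further confirmation". Both zones of the rule are creatinine concentrations.

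Section 8 gives the matching analysis: "Proportion of patients correctly identified to have CKD" with eGFR below 60 is to be reported, and "Sensitivity and Specificity of different Cr thresholds calculated". Neither section mentions age or sex.

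Four other places bear on this:
- Section 3: "Participants will be selected purposively to include a range of age, gender, ethnicity" and severity of renal disease. Demographics are recorded.
- Section 6.1: the only age criterion is "Is 18 years of age or older".
- Section 2.1: the Study A primary objective is "To compare estimated glomerular filtration rate (eGFR) using POC-Cr and serum Cr with formal GFR assessment in people of different ethnicities", so eGFR will be calculated from POC-Cr in any case.
- Section 1: "Recently, use of ethnicity in kidney function testing has been recommended to be removed".

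The protocol gives no eGFR equation, target sensitivity or specificity, or expected miss rate.

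**The concern.** The eGFR that corresponds to a given creatinine depends on age and sex in the standard equations. Within one ethnic group, the creatinine equivalent to eGFR 60 therefore differs between a young man and an old woman by far more than a small assay error. The sample is deliberately spread over the two variables for which the rule makes no provision.

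Two consequences follow. First, sensitivity, specificity and the width of the confirmation range would reflect age and sex spread as well as device performance. Second, two ethnic groups with identical physiology and a perfect device would get different best cut-offs if one were older or had more women. The study would then report an ethnic difference that is really one of case mix, on the very question it sets out to answer. Cut-offs obtained this way would also transfer poorly to community screening, where the mix is different again.

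**Working it through.** There is no figure in the protocol to reproduce. The check asks how far a single creatinine cut-off can go wrong with no device error.

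**Assumptions (not in the protocol).** CKD-EPI 2021 creatinine equation, 50% women, and the GFR and age distributions stated below.

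**Step 1: creatinine at eGFR 60.** Above the equation's knot, with κ = 0.9 mg/dL (men) or 0.7 mg/dL (women):

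creatinine (µmol/L) = 88.4 × κ × (142 × 0.9938^age × [1.012 if female] / 60)^(1/1.2)

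- Man, 20: 88.4 × 0.9 × (142 × 0.883 / 60)^(0.833) = 147
- Man, 80: 108
- Woman, 20: 116
- Woman, 80: 88.4 × 0.7 × (142 × 0.608 × 1.012 / 60)^(0.833) = 85

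The ratio of the extremes is 147 / 85 = 1.73.

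**Step 2: one cut-off, error-free device, 95% specificity.** Simulation of 400,000 people per scenario: GFR normal with mean 60 or 75 and SD 25, truncated; age 18-85, 30-80 or 40-75; 27-49% below 60. The cut-off is the 95th percentile of creatinine among those at or above 60.

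| Group | Share of low-eGFR participants ruled in |
|---|---|
| All | 70-78% |
| Women | 50-58% |
| Men | 90-99% |

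Not ruled in: 100 − 78 = 22% to 100 − 70 = 30%.

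**Step 3: dependence on the operating point.** A wider set of scenarios (eGFR N(50,20), N(60,25), N(70,25), N(80,20), N(90,20) and uniform 15-120; age 45±12, 55±15 or 60±10) gives these shares not ruled in:

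| Cut-off chosen by | Not ruled in |
|---|---|
| Youden index | 5-22% |
| 90% specificity | 7-23% |
| 95% specificity | 12-33% |
| 97.5% specificity | 15-41% |
| 99% specificity | 19-51% |

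**Step 4: the planned confirmation range.** Let the range run from the cut-off with 95% sensitivity to the one with 95% specificity. In the Step 2 scenarios it holds 17-26% of all participants. By construction only 5% of low-eGFR participants lie below it, so of the 22-30% not ruled in, 22 − 5 = 17 to 30 − 5 = 25 percentage points go to confirmation. With 97.5% limits in the Step 3 scenarios the range holds 13-32% of participants, and 2.5% of low-eGFR participants lie below it.

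**Step 5: artefactual ethnic difference.** Same equation, no device error. A group that is 65% female and aged 50-85 has a Youden cut-off of about 96 µmol/L. A group that is 35% female and aged 30-65 has one of about 124 µmol/L. The difference of 28 µmol/L is due to age and sex mix alone.

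**Step 6: gain from the fix, judged against formal GFR.** Added assumptions: 15-20% lognormal error of the equation around formal GFR, and 8% device CV. At 95% specificity, a raw creatinine cut-off has sensitivity 55-66% and a cut-off on POC-based eGFR 66-76%. Taken scenario by scenario, the gain is about 8-15 points.

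**The case against.** The strongest reply has four parts.

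- **The size of the loss is not a property of this protocol.** It needs an outside equation, an assumed case mix and a chosen specificity. This stands. A reader might infer that even an error-free device would miss about a quarter of low-eGFR participants. The documents do not support that as a fixed figure: Step 3 runs from about 5% to over 50%. Nor is it a miss rate, because section 2.2 plans a confirmation range that would catch many of those not ruled in.
- **Ethnicity alone is an inference from silence.** The protocol does not say that age and sex are excluded, section 8 speaks of thresholds in the plural, and an SAP could stratify. This stands in part. However, the quantity on which the rule is set is written into the objective, and an SAP that moved the rule to POC-based eGFR would depart from it.
- **The advantage of POC-based eGFR is easily overstated.** Scored against eGFR from the same equation, with 8% device CV, it reaches about 90% sensitivity against 67-75% for raw creatinine. That comparison is circular, since without device error the first figure is 100% by construction. Step 6 is the fair comparison and shows a smaller gain, with POC-based eGFR itself still failing to rule in 24-34%.
- **The target need not be creatinine-based.** A reader might infer that the cut-off would merely re-measure assay agreement because eGFR comes from creatinine. The protocol does not say which eGFR is meant. Section 3 applies the label eGFR to the filtration panel, and section 8 plans agreement against 99mTc-DTPA and the panel. That reading is not supported; the target only needs to be named.

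It is also fair to say that this is a secondary objective in work the protocol calls preliminary.

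**Conclusion.** The point holds as a cheap improvement to a choice the protocol states. If eGFR depends on age and sex, one creatinine cut-off per ethnic group misclassifies people without any device error, and a difference between ethnic cut-offs cannot be attributed to ethnicity. Under CKD-EPI 2021 the relevant creatinine spans about 85 to 147 µmol/L. At 95% specificity in clinic-like mixes, about 22-30% of low-eGFR participants are not ruled in, and most of the shortfall is in women. Much of the cost is a wide grey zone, holding roughly 13-32% of participants depending on how its limits are set.

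The direction of these results needs only an equation that uses age and sex. The sizes rest on the assumed equation, case mix, sex ratio and operating point, and should be quoted as ranges. The choice also sits awkwardly with the protocol's own remark in section 1 on removing ethnicity from kidney function testing, since ethnicity is the one covariate the threshold names.

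**What to change.** Amend the threshold objective in the Study Summary and section 2.2, and the matching sentences in section 8:

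- Define the rule-in threshold and the confirmation range on eGFR calculated from POC-Cr with age and sex, which the primary objective already requires, or as age- and sex-specific POC-Cr values. Report performance by ethnicity.
- Name the target as formal GFR below 60 by 99mTc-DTPA or the filtration panel, as collected in Study A, with serum-creatinine eGFR below 60 as a secondary target.
- If a creatinine figure is wanted for field use, give it as an age-by-sex table derived from the eGFR threshold.

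Sex-specific creatinine cut-offs alone would recover part of the loss. Under the assumed equation (age 55±15, error-free device, serum eGFR as target), 9-11% would not be ruled in at 95% specificity and 14-20% at 97.5%.

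The cost is a change of wording. Demographics are already recorded, so no new data or visits are needed. The downside is that field users must enter age and sex or consult a table.

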Study A: POC-Cr will be assessed using the NovaMaxCreat and Epoc devices. Finger-prick capillary whole blood samples will be taken (0.05 uL for NovaMaxCreat and 0.9 uL for Epoc) using lancets by the research team. Venous serum creatinine for routine care (Isotope Dilution Mass Spectrometry (IDMS) Traceable Enzymatic assay) and ^{99m}Tc-DTPA glomerular filtration rate testing (where available) will be extracted from hospital laboratory databases. Participants not undergoing routine ^{99m}Tc-DTPA glomerular filtration rate testing will also have a 'eGFR filtration panel assessment – Beta-2-microglobulin, cystatin-C (processed by Synlab/ViaPath) and beta-trace-protein concentration (processed by Affinity laboratories), assessment on their venous blood sample.

Participants will be trained to use the POC-Cr device by the research team and time taken recorded and asked to perform one POC-Cr test.

In addition, the Epop Blood Analysis system, will also measure capillary potassium concentrations, which will be compared to serum potassium (taken from the venous blood sample for routine clinical care). This will be tested in the laboratory using the Roche Chemistry Analyser Cobas 8000.

Study B: Participants will be trained to use the POC-Cr device, NovaMaxCreat (NovaBio) by the research team and time taken recorded. Participants will be taught how to perform quality controls. All sample results will be digitally recorded by the device and downloaded after the device is returned. Participants will be asked to do one test at the hospital (with a simultaneous lab creatinine on site for validation), then to self-monitor four times per day (first thing in morning, midday, before evening meal/early evening, before bed) and each test recorded in a paper diary or electronically as desired. Details reported will include date and time of test, test success, device and non-device failures (test results, missed testing and reasons for missed test (e.g. forgot, did not want to test) and adverse events (e.g. pain or infection or prolonged injury after sampling, pre-syncopal or syncopal episode).

For participants who perform finger-prick testing for capillary blood glucose monitoring, both samples (creatinine using NovaMaxCreat and glucose using their usual device) can be taken from the same finger-prick test. However, participants will be advised to take the creatinine sample first.

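### The Study A POC-Cr threshold is set against an eGFR below 60 of unnamed source, most naturally creatinine-based, so test and label share an input although a DTPA or panel reference is already collected

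*Protocol*

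**What the plan says.** Protocol section 2.2 (and the matching objective in the Study Summary) seeks a "threshold of POC-Cr concentration in people of different ethnicities which are confirmatory of eGFR" below 60 mL/min/1.73m², plus a range of POC-Cr values needing confirmation. Section 8 gives two analyses for this. One is "Proportion of patients correctly identified to have CKD", again defined by eGFR below 60. The other reads "Sensitivity and Specificity of different Cr thresholds calculated". Neither names the reference that supplies the label.

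Other sections bear on what eGFR means:

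- Section 2.1, primary objective: "To compare estimated glomerular filtration rate (eGFR) using POC-Cr and serum Cr with formal GFR assessment in people of different ethnicities". Here eGFR comes from creatinine and formal GFR is the comparator.
- Section 6.2 excludes people whose formal test was requested only because estimated GFR was thought not to reflect true GFR, so it separates the two ideas.
- Section 3: "glomerular filtration rate testing (where available) will be extracted from hospital laboratory databases". Participants without DTPA have a panel of beta-2-microglobulin, cystatin-C and beta-trace-protein, which that section also calls an eGFR panel.
- Section 8 lists the reference standards for analytical error as "IDMS enzymatic traceable and 99mTc-DTPA and GFR filtration panel".

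**The concern.** If the label is a creatinine-based eGFR, whatever changes creatinine without changing GFR, such as muscle mass, moves test and label together and counts as correct classification. The cut-off then looks more accurate for kidney function than it is.

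The ethnicity question is the most exposed. Section 1 notes that "use of ethnicity in kidney function testing has been recommended to be removed". With an equation that has no ethnicity term, the same creatinine, age and sex give the same eGFR in every group. The threshold can then differ between groups only a little, through device bias, case mix or measurement noise. With an ethnicity term, the difference largely returns the coefficient that was put in. Similar thresholds across groups could be mistaken for evidence that one cut-off serves all, in a study whose overall aim is community screening focused on ethnic minority groups.

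**Working it through.** **Step 1: which eGFR is meant?** The protocol states no figure for this objective that could be reproduced, so the first check is textual.

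- Section 2.1 ties eGFR to POC-Cr and serum creatinine and contrasts it with formal GFR.
- Section 6.2 contrasts estimated with true GFR.
- Section 3 gives the panel only to participants without routine DTPA. A panel-based eGFR would therefore leave the DTPA participants without a label. Among the tests listed, only a creatinine-based eGFR can cover all 375.

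A creatinine-based label is the natural reading, but it is an inference.

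**Step 2: how much does it matter?** All inputs below are assumptions; none comes from the protocol. Both models omit age and sex.

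*Model 1* (1,000,000 per scenario). GFR is log-normal, median 60, log-SD 0.40.

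- ln Cr = −ln GFR + s + N(0, 0.12 or 0.18), where s is the ethnic shift at equal GFR
- eGFR = 1/Cr
- ln POC = ln Cr + N(0, 0.07)
- The cut-off is set at 95% specificity against eGFR below 60.

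| | Sensitivity | Specificity |
|---|---|---|
| Scored against eGFR below 60, s = 0 | 94–95% | 95% |
| Same cut-off against true GFR below 60, s = 0 | 86–89% | 86–90% |
| eGFR-based cut-off against true GFR, s = 0.10 | 93–96% | 76–79% |

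With no shift the inflation is 95 − 90 = 5 to 95 − 86 = 9 points of specificity. For sensitivity it is 94 − 89 = 5 to 95 − 86 = 9 points. With s = 0.10 the eGFR-based cut-off moves about 1%, while the cut-off needed against true GFR moves about 10–11%. In that group specificity falls and sensitivity rises, so the error is a shift of operating point and not a loss on both sides.

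*Model 2* (400,000 per scenario). GFR is log-normal, median 60, log-SD 0.45.

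- Cr = 100 × g × (GFR/60)^(−1/1.2) × 12% noise, where g is the ethnic shift
- eGFR = 60 × (Cr/100)^(−1.2)
- POC = Cr × (1 + b) × 10% noise, where b is device bias
- The cut-off maximises the Youden index.

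| Ethnic shift, device bias | Cut-off: true GFR | Cut-off: serum-Cr eGFR | Cut-off: POC-Cr eGFR |
|---|---|---|---|
| 0%, 0% | 100.4 | 99.7 | 99.9 |
| 5%, 0% | 105.2 | 100.7 | 100.0 |
| 10%, 0% | 110.5 | 101.6 | 100.1 |
| 20%, 0% | 119.9 | 103.4 | 100.2 |
| 0%, 8% | 108.4 | 108.1 | 99.9 |

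- For a 10% shift the cut-off moves 110.5/100.4 = 1.10 (10%) with a GFR target and 101.6/99.7 = 1.02 (2%) with a serum-creatinine eGFR target.
- With no shift or bias, sensitivity/specificity is 0.870/0.878 against GFR and 0.923/0.918 against serum-creatinine eGFR. The inflation is 5.3 and 4.0 points. Against POC-Cr eGFR it is about 1.00/1.00.
- An 8% device bias moves the serum-eGFR cut-off by 108.1/99.7 = 1.08. A device difference is therefore visible with a serum label. With a POC-Cr label it is not (99.9 in both rows).

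**The case against.** The strongest reply is that circularity is inferred. Section 3 also uses eGFR for a panel with no creatinine among its listed markers. Section 8 calls for categorical agreement of POC-Cr with its reference standards, and the threshold sentences close that same Study A text. Scoring them against DTPA or the panel is tenable, and an analysis plan that is not shown might say so. This stands as far as it goes: the source is unnamed. But the target condition is written into the objective itself, and a panel-based eGFR would not cover the DTPA participants, so rewording is needed on either reading.

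Three stronger readings are tempting, and the protocol does not support them.

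- A reader might infer that formal, measured GFR exists for every Study A participant. DTPA is used only where available. The rest have a panel, which is itself an estimate. What everyone has is one of two reference tests.
- A reader might infer that the threshold cannot reveal any ethnic difference. A serum-creatinine label would still show ethnic differences in device bias, and section 1 names device performance across ethnicities as a gap.
- A reader might infer that the study is blind to ethnic differences in the creatinine–GFR relation. The primary objective compares both eGFRs "with formal GFR assessment in people of different ethnicities", and a 10% shift should appear there as bias. That comparison yields no POC-Cr cut-off, however, so it does not repair the threshold.

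**Conclusion.** The concern holds in a limited form. The threshold, confirmation range, sensitivity/specificity and correct-identification analyses are tied to an eGFR below 60 whose source is not stated and which, on the protocol's own usage, is most naturally creatinine-based. On that reading, apparent accuracy is inflated by about 4 to 9 points with a serum label, and approaches 100% with a POC-Cr label. Most of an ethnic difference in creatinine at equal GFR is hidden from the threshold. The direction follows from test and label sharing an input. The sizes depend on assumed GFR spread, non-GFR creatinine scatter, device noise and ethnic shift. Because the models omit age and sex, the near-100% figure is best read as an upper limit for a single creatinine cut-off.

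The objective is secondary and no data are lost, so this should be fixed before analysis but does not threaten the primary comparison.

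**What to change.** In the Study Summary objective, section 2.2 and section 8:

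- Define the target condition for the threshold, confirmation range, sensitivity, specificity and correct-identification analyses as GFR below 60 mL/min/1.73m² by the participant's own reference test: 99mTc-DTPA, or the three-marker panel.
- Report results separately by reference type, because the panel is itself an estimate.
- Keep serum-creatinine eGFR below 60 as a secondary analysis, described as agreement with routine eGFR and not as detection of reduced kidney function.
- Do not use eGFR calculated from POC-Cr as a label.

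The cost is a wording amendment with no new data or visits. Reported sensitivity and specificity will probably be lower, and splitting the 375 participants by reference type, and again by ethnicity, reduces precision in each part.
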